10.3.1 Summary Tables for Adverse Events

All pre-dose AEs (as defined in [Section 10.3](#)) will be excluded from the summary tables but will be listed for all subjects.

Descriptive statistical methods will be used to summarize the TEAE data.

The number and percentage of subjects reporting each TEAE will be summarized for both SOC and PT. For summaries by SOC and PT, with the exception of TEAEs by severity and relationship to IMP, the number of subjects and the number of events will be summarized. For summaries by severity and relationship only the number of subjects will be summarized.

For counts of subjects experiencing events the following will apply:

- a subject experiencing TEAEs in more than one body system, for a treatment, will be counted once in the total number of subjects with TEAEs in that study period;
- a subject with more than 1 TEAE in the same SOC, for a treatment, counts only once at the SOC level;
- a subject with more than 1 TEAE in the same PT, for a treatment, counts only once at the PT level.

For event counts, all events are included.

When it is necessary to calculate percentages, the denominator will be the total number of subjects in the safety analysis population for that treatment or study part/period and the numerator will be the total number of subjects reporting a TEAE within the relevant category.

Summaries presented for SOC and PT will be presented in descending order of frequency overall i.e., most frequently reported SOC in the study and then by most frequently reported PT in the study within each SOC.

10.3.1.1 Overall Summary of Adverse Events

The following will be summarized by treatment:

- number and percentage of subjects reporting at least 1 TEAE
- number and percentage of subjects reporting at least 1 severe TEAE
- number and percentage of subjects reporting at least 1 life-threatening TEAE
- number and percentage of subjects reporting at least 1 IMP-related TEAE
- number and percentage of subjects reporting at least 1 AE of special interest
- number and percentage of subjects reporting at least 1 serious TEAE
- number and percentage of subjects reporting at least 1 TEAE leading to death
- total number of TEAEs
- total number of severe TEAEs
- total number of life-threatening TEAEs
- total number of IMP-related TEAEs
- total number of AEs of special interest
- total number of serious TEAEs
- total number of TEAEs leading to death

10.3.1.2 Summary of Treatment-Emergent Adverse Events by System Organ Class and Preferred Term

All subjects reporting TEAEs will be summarized by treatment. Counts will be given for number of subjects and number of events. Subjects experiencing more than one TEAE within a treatment will be counted only once for number of subjects but will be counted more than once for number of events.

Additionally, subjects reporting TEAEs will be summarized for SOC and PT by treatment. Counts will be given for number of subjects and number of events. For programming purposes counts of number of subjects will be by maximum severity i.e., subjects experiencing more than one episode of a TEAE within a treatment will be counted only once within each SOC and PT using the most severe episode.

10.3.1.3 Summary of Treatment-Emergent Adverse Events by Severity

All subjects reporting TEAEs will be summarized by severity (i.e., mild, moderate, severe, life-threatening or death) and treatment. Counts will be given for number of subjects, not number of events. Counts will be given by maximum severity (i.e., subjects experiencing more than one TEAE within a treatment will be counted only once using the most severe episode).

Additionally, subjects reporting TEAEs will be summarized for SOC and PT by maximum severity (i.e., mild, moderate, severe, life-threatening or death) and treatment. Counts will be given for total number of subjects, not for events. Counts by maximum severity will be given (i.e., subjects experiencing more than one TEAE within a treatment will be counted only once within each SOC and PT using the most severe episode).

10.3.1.4 Summary of Treatment-Emergent Adverse Events by Relationship to IMP

All subjects reporting TEAEs will be summarized by relationship to IMP (i.e., "YES" and "NO") and treatment. Counts will be given for number of subjects, not number of events. Counts will be given by the closest relationship to IMP (i.e., subjects experiencing more than one TEAE within a treatment will be counted only once using the most closely related event).

Additionally, subjects reporting TEAEs will be summarized for SOC and PT by closest relationship to IMP (i.e., "YES" and "NO") and treatment. Counts will be given for total number of subjects, not for events. Counts by closest relationship will be given (i.e., subjects experiencing more than one TEAE within a treatment will be counted only once within each SOC and PT using the most closely related event).

10.3.1.5 Summary of IMP-related TEAEs

All subjects reporting IMP-related TEAEs will be summarized by treatment. Counts will be given for number of subjects and number of events. Subjects experiencing more than one IMP-related TEAE within a treatment will be counted only once for number of subjects but will be counted more than once for number of events.

Additionally, subjects reporting IMP-related TEAEs will be summarized for SOC and PT by treatment. Counts will be given for number of subjects and number of events. For programming purposes counts of number of subjects will be by maximum severity i.e., subjects experiencing more than one episode of an IMP-related TEAE within a treatment will be counted only once within each SOC and PT using the most severe episode.

10.3.1.6 Summary of Adverse Events of Special Interest

All subjects reporting AEs of special interest will be summarized by treatment. Counts will be given for number of subjects and number of events. Subjects experiencing more than one AE of special interest within a treatment will be counted only once for number of subjects but will be counted more than once for number of events.

Additionally, subjects reporting AEs of special interest will be summarized for SOC and PT by treatment. Counts will be given for number of subjects and number of events. For programming purposes counts of number of subjects will be by maximum severity i.e., subjects experiencing more than one episode of an AE of special interest within a treatment will be counted only once within each SOC and PT using the most severe episode.

10.3.1.7 Summary of Serious Adverse Events

All subjects reporting SAEs will be summarized by treatment. Counts will be given for number of subjects and number of events. Subjects experiencing more than one SAE within a treatment will be counted only once for number of subjects but will be counted more than once for number of events.

Additionally, subjects reporting SAEs will be summarized for SOC and PT by treatment. Counts will be given for number of subjects and number of events. For programming purposes counts of number of subjects will be by maximum severity i.e., subjects experiencing more than one episode of a SAE within a treatment will be counted only once within each SOC and PT using the most severe episode.

10.3.2 Listings for Adverse Events

All pre-dose AEs (as defined in [Section 10.3](#)) will be listed, including SOC and PT.

A separate data listing of all TEAEs will be provided including the SOC and PT. In addition, listings of all AEs of special interest and SAEs will be provided.

10.4 Laboratory Evaluations

The details of sample collection for laboratory safety analysis are described in the study protocol.

Where a value is provided by the safety laboratory as either above or below the limit of detection (LOD) this will be set to the LOD itself for summary purposes. No imputations will be made in the individual listings.

10.4.1 Summary Tables for Laboratory Evaluations

Hematology and coagulation, and serum biochemistry will be summarized (mean, SD, median, minimum, maximum and n) for each laboratory parameter at each time point, including changes from baseline (Day -1, Admission in each study period) at each 96 h post-baseline time point by treatment.

Shift tables from baseline to each post-baseline time point (with respect to the number and percentage of subjects with values below, within or above the reference range) will be presented by treatment. Percentages will be based on the number of subjects with measurements at baseline and the relevant 96 h post-baseline time point.

Reference ranges for each laboratory parameter will be presented for the relevant parameter in each summary table.

10.4.2 Listings for Laboratory Evaluations

The sample collection data and comments (e.g., collection times) for laboratory analysis and urinalysis data will be listed.

All individual subject data, for planned hematology and coagulation, serum biochemistry and urinalysis data will be listed, including change from baseline. If applicable, data from unscheduled laboratory tests will also be listed and flagged with a “#” to indicate it will not be used in the summary statistics. In these listings, individual data will be flagged with an “H” or an “L” for values that are higher or lower than their reference ranges, respectively.

Separate listings by subject of all hematology and coagulation, serum biochemistry and urinalysis values outside their reference ranges will also be provided. References ranges will be supplied by the safety laboratory for hematology and coagulation, and serum biochemistry and per the eCRF for urinalysis (i.e., a positive or negative result) with the exception of the following reference ranges for urinalysis:

- pH: 5.0 to 8.0
- Specific gravity: 1.000 to 1.030

10.5 Vital Signs

The details of measurement of supine vital signs are described in the study protocol.

10.5.1 Summary Tables for Vital Signs

Vital signs data (i.e., systolic and diastolic blood pressure [BP], pulse rate and oral temperature), including change from baseline (Day 1, Pre-dose of each treatment period) will be summarized (i.e., mean, SD, median, minimum, maximum and n) at each post-baseline time point by treatment.

In addition, the number of subjects with ‘substantial’ increases (“INC”) or decreases (“DEC”) or no substantial change (“NONE”) from baseline in systolic BP ($>\pm 20$ mmHg), diastolic BP ($>\pm 10$ mmHg) and pulse rate ($>\pm 15$ bpm) will be summarized.

10.5.2 Listings for Vital Signs

All individual vital signs data (i.e., systolic and diastolic BP, pulse rate and oral temperature) data will be listed, including change from baseline. Individual data will be flagged with an “H” or an “L” for values that are higher or lower than their reference ranges, respectively, and subjects with ‘substantial’ increases or decreases from baseline (as defined in [Section 10.5.1](#)) in systolic BP, diastolic BP and pulse rate will be flagged with an “I” (increase) or “D” (decrease), respectively. If applicable, data from unscheduled vital signs assessments will also be listed and flagged with a “#” to indicate it will not be used in the summary statistics.

In addition, a separate listing of all vital signs data outside their reference ranges by subject will also be provided.

The reference ranges taken from Quotient SOP “The Interpretation of the Electrocardiogram, Vital Signs and Clinical Laboratory Data During Phase I / II Clinical Trials” for oral body temperature and from the exclusion criteria of the protocol for all other vital signs parameters, as defined in [Table 5](#), will be used.

Table 5 Vital Signs Reference Ranges

Parameter	Lower limit	Upper limit
Systolic BP	90 mmHg	140 mmHg
Diastolic BP	50 mmHg	90 mmHg
Pulse rate	40 bpm	90 bpm
Oral Body Temperature	35.5°C	37.5°C

NA=Not applicable

10.6 ECGs

The details of measurement of supine ECG parameters (i.e., ventricular rate, RR interval, uncorrected QT interval, QTcF interval, PR duration, QRS interval, QRS axis, rhythm and interpretation) are described in the study protocol. ECG parameters will be reported in the order given above i.e., both summary tables and data listings.

10.6.1 Summary Tables for ECGs

ECG data, including change from baseline (Day 1, Pre-dose of each treatment period), will be summarized (i.e., mean, SD, median, minimum, maximum and n) at each post-baseline time point by treatment.

The number and percentage of subjects with normal and prolonged QT intervals corrected for heart rate using Fridericia's correction (i.e., QTcF) and increases in QTcF intervals from baseline within the categories defined in [Table 6](#) (based on the International Council on Harmonization [ICH] E14 guideline [\[2\]](#)) will be summarized by time point. Percentages will be based on the number of subjects with measurements at the relevant time point.

Table 6 ICH E14 Ranges for QTcF Intervals

Parameter	ICH E14 Range
QTcF intervals	≤450 msec (normal)
	451-480 msec
	481-500 msec
	>500 msec
Increase in QTcF interval from baseline	<30 msec
	30-60 msec
	>60 msec

10.6.2 Listings for ECGs

All ECG measurements, including derivations such as change from baseline will be listed.

All ECG measurements will be flagged with an "H" or an "L" for values that are higher or lower than their reference ranges, respectively. If applicable, data from unscheduled ECG assessments will also be listed and flagged with a "#" to indicate it will not be used in the summary statistics.

In addition, subjects with increase in QTcF interval from baseline (30-60 msec) and with 'substantial increases' (>60 msec) will be flagged with 'I' and 'SI', respectively.

A separate listing of all ECG parameters outside their reference range by subject will also be provided.

The reference ranges taken from the exclusion criteria of the protocol for ventricular rate and from Quotient SOP "The Interpretation of the Electrocardiogram, Vital Signs and Clinical Laboratory Data During Phase I / II Clinical Trials" for all other ECG parameters, as defined in [Table 7](#), will be used, apart from the reference range for RR interval which is calculated by the following formula:

$$\text{RR interval} = \frac{60000}{\text{heart rate}}$$

Table 7 ECG Reference Ranges

Parameter	Split	Lower limit	Upper limit
Ventricular Rate	NA	40 bpm	90 bpm
RR Interval	NA	600 msec	1500 msec
QT Interval	NA	0 msec	500 msec
QTcF Interval	NA	0 msec	450 msec
PR Interval	NA	120 msec	220 msec
QRS Duration	NA	0 msec	120 msec
QRS Axis	NA	-30°	100°
Rhythm	NA	Sinus rhythm, Sinus bradycardia (rate dependent), Sinus arrhythmia	

HR=heart rate

NA=Not applicable

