2.2 SAFETY OBJECTIVE (SECONDARY STUDY OBJECTIVE)

The safety (secondary) objective for this study is to explore the safety and tolerability of a single oral dose of entrectinib in healthy volunteers on the basis of the following endpoints:

- Incidence and severity of adverse events,
- Incidence of abnormalities in laboratory safety tests, physical examinations, 12-lead ECGs and vital sign measurements

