4.5.6 Electrocardiograms

Single ECG recordings will be obtained at specified time points, as outlined in the schedule of activities (see [Appendix 1](#)). The acceptable deviations from the nominal ECG measurement time points are:

- The pre-dose ECG measurements will be taken ≤ 2 hours before dosing
- Post-dose ECG measurements will be taken ± 15 minutes from the nominal post-dose time point
- Discharge ECG measurements will be taken ± 1 hour from the nominal time point.
- For return visits ECG measurements will be taken ± 4 hours from the nominal return visit time point.

ECGs acquired on different days should be as closely time-matched as feasible. ECG recordings may be obtained at unscheduled time points as indicated. The Day 1, pre-dose assessment in each period will be used as baseline.

Entrectinib—Genentech, Inc.
36/Protocol GP41341, Version 1 – 02 April 2019

All ECG recordings must be performed using a standard high-quality, high-fidelity digital electrocardiograph machine equipped with computer-based interval measurements. Lead placement should be as consistent as possible. ECG recordings must be performed after the subject has been resting in a supine position for at least 5 minutes. All ECGs are to be obtained prior to other procedures scheduled at that same time (e.g., vital sign measurements, blood draws) and should not be obtained within 3 hours after any meal, whenever feasible. Circumstances that may induce changes in heart rate, including environmental distractions (e.g., television, radio, conversation), should be avoided during the pre-ECG resting period and during ECG recording.

For safety monitoring purposes, the investigator must review, sign, and date all ECG tracings. Paper copies of ECG tracings will be kept as part of the subject's permanent study file at the site. The following should be recorded in the appropriate eCRF: heart rate, RR interval, QRS interval, PR duration, uncorrected QT interval, and QTcF based on the machine readings of the individual ECG tracings. Any morphologic waveform changes or other ECG abnormalities must be documented on the eCRF. If considered appropriate by the Sponsor, ECGs may be analyzed retrospectively at a central laboratory.

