If at a particular post dose time point the mean QTcF is >500 ms and/or 60 ms longer than the baseline value, another ECG must be recorded, ideally within the next 5 minutes, and ECG monitoring should continue until QTcF has stabilized on two successive ECGs. The Medical Monitor should be notified. Standard-of-care treatment may be instituted per the discretion of the investigator. If a pharmacokinetic sample is not scheduled for that time point, an unscheduled pharmacokinetic sample should be obtained. A decision on study drug discontinuation should be made, as described in Section 4.6.1. The investigator should also evaluate the subject for potential concurrent risk factors (e.g., electrolyte abnormalities, co-medications known to prolong the QT interval, severe bradycardia).

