4.6 TREATMENT, SUBJECT, STUDY, AND SITE DISCONTINUATION

4.6.1 Stopping Criteria

The study will be halted, and the risk to other subjects evaluated if any of the following criteria are met:

- A serious adverse reaction (i.e., a serious adverse event considered at least possibly related to the IMP administration) in one subject.
- Severe non-serious adverse reactions (i.e., severe non-serious adverse events considered at least possibly related to the IMP administration) in two subjects in the

Entrectinib—Genentech, Inc.
37/Protocol GP41341, Version 1 – 02 April 2019

same cohort of the study, independent of within or not within the same system organ class.

Relatedness will be determined by the investigator.

If the study is halted, a temporary halt will be submitted to the Medicines and Healthcare products Regulatory Agency (MHRA) and ethics committee (EC) in the form of a substantial amendment. The study may be resumed or terminated; however, it will not be resumed until a further substantial amendment to resume the study is submitted and approved by MHRA and EC.

In addition, subjects must permanently discontinue study treatment if they experience any of the following:

- Any medical condition that the investigator or Sponsor determines may jeopardize the subject's safety if he or she continues to receive study treatment
- Investigator or Sponsor determination that treatment discontinuation is in the best interest of the subject
- Pregnancy
- Concurrent illness or requirement for prohibited medication
- Experiencing a serious or severe adverse event including but not limited to:
 - corrected QT interval by Fridericia's formula (QTcF) interval of >500 msec or increase in QTcF interval of >60 msec from baseline (confirmed following a repeat ECG)
 - ALT concentration >3 × the upper limit of the reference range

The primary reason for study treatment discontinuation should be documented on the appropriate eCRF.

For a subject who withdraws because of an IMP-related adverse event, every effort will be made to ensure the subject completes follow-up procedures. Any subject withdrawn or discontinuing the study prematurely because of an IMP-related adverse event or termination of the study will be considered to have completed the study, and will not be replaced. Subjects who discontinue study treatment may be replaced at the discretion of the Sponsor and the investigator to ensure a minimum of 12 evaluable subjects in each study part.

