14.5.1.2.1	ECGs Summary Statistics: Safety Analysis Population Part 1 <Parameter>
14.5.1.2.2	ECGs QTcF Categorical Data Summary Statistics: Safety Analysis Population Part 1
14.5.1.3	Palatability Evaluations Summary Statistics: Safety Analysis Population <Palatability Question> Part 1

Table Number	Table Title
14.5.2.1	Vital Signs Summary Statistics: Safety Analysis Population Part 2 <Parameter>
14.5.2.2.1	ECGs Summary Statistics: Safety Analysis Population Part 2 <Parameter>
14.5.2.2.2	ECGs QTcF Categorical Data Summary Statistics: Safety Analysis Population Part 2

19 Index of Figures

Figure Number	Figure Title
	Plasma Pharmacokinetic Concentrations and Parameters
14.2.1.1.1	
Plasma Pharmacokinetic Concentrations: Entrectinib Linear/Linear Scale Arithmetic Mean (\pm Arithmetic SD) Values: PK Population Part 1
 
(programming note: all treatments on same plot)
 
(programming note: where concentrations are provided as ng/mL, these will be converted to nmol/L)

14.2.1.1.2	
Plasma Pharmacokinetic Concentrations: M5 Linear/Linear Scale Arithmetic Mean (\pm Arithmetic SD) Values: PK Population Part 1
 
(programming note: all treatments on same plot)
 
(programming note: where concentrations are provided as ng/mL, these will be converted to nmol/L)

14.2.1.1.3	
Plasma Pharmacokinetic Concentrations: Entrectinib and M5 Linear/Linear Scale Arithmetic Mean (\pm Arithmetic SD) Values: PK Population Subtitle: <Treatment> Part 1
 
(programming note: where concentrations are provided as ng/mL, these will be converted to nmol/L)

14.2.1.1.4	
Plasma Pharmacokinetic Concentrations: Entrectinib Linear/Linear Scale Spaghetti Plots of All Individual Values: PK Population Subtitle: <Treatment> Part 1
 
(programming note: where concentrations are provided as ng/mL, these will be converted to nmol/L)

14.2.1.1.5	
Plasma Pharmacokinetic Concentrations: M5 Linear/Linear Scale Spaghetti Plots of All Individual Values: PK Population Subtitle: <Treatment> Part 1
 
(programming note: where concentrations are provided as ng/mL, these will be converted to nmol/L)

Figure Number	Figure Title

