	2 H	xx	xx (xx.x)	xx (xx.x)	xx (xx.x)	xx (xx.x)	xx (xx.x)	xx (xx.x)	xx (xx.x)
	6 H	xx	xx (xx.x)	xx (xx.x)	xx (xx.x)	xx (xx.x)	xx (xx.x)	xx (xx.x)	xx (xx.x)
	48 H	xx	xx (xx.x)	xx (xx.x)	xx (xx.x)	xx (xx.x)	xx (xx.x)	xx (xx.x)	xx (xx.x)
	96 H	xx	xx (xx.x)	xx (xx.x)	xx (xx.x)	xx (xx.x)	xx (xx.x)	xx (xx.x)	xx (xx.x)

Note: The data in this table are presented in listing xx
Each treatment comprised of a 600 mg oral dose of entrectinib administered in the fed state.
BASELINE is defined as Day 1, Pre-dose for each treatment period.
Categories for QTcF interval and QTcF interval increases are based on ICH E14 guidelines.
N# is the total number of subjects in the relevant treatment and is used as the denominator for
the percentages of subjects, n indicates the number of subjects with observations at the given time point.

PROGRAM PATH: X:\~\QSC201525\~\TFLS\PRODUCTION\TAB_XX

DDMMYYYY HH:MM

(Programming note: This table will be continued for all treatments.)
(Programming note: A similar table will be produced for Part 2 ECGs, i.e., Table [14.5.2.2.2]. Treatments
will be 200 mg F06 coarse and 200 mg F06 fine and footnote will state: Each treatment comprised of a 200 mg oral
of entrectinib administered in the fasted state.)

Genentech, Inc.
Protocol: GP41341

Page x of y

TABLE 14.5.1.3
Palatability Evaluations
Summary Statistics: Safety Analysis Population
<Palatability Question>
Part 1

Statistic	600 mg F15 (N=XX)	600 mg F16 (N=XX)	600 mg F06 (N=XX)
	n (%)	n (%)	n (%)
Mean	xx.x	xx.x	xx.x
SD	xx.x	xx.x	xx.x
Median	xx.x	xx.x	xx.x
Min	xx	xx	xx
Max	xx	xx	xx
n	xx	xx	xx

Note: The data in this table are presented in listing xx
Each treatment comprised of a 600 mg oral dose of entrectinib administered in the fed state.
Acceptability and each palatability attribute will be scored using 0 mm = "I did not like it" through
to 100 mm = "I liked it very much".

[figure not shown]
PROGRAM PATH: X:\~\QSC201525\~\TFLS\PRODUCTION\TAB_XX DDMMYYYY HH:MM

(Programming note: A separate page will be used for each palatability question with the relevant subheading.
Footnote on scoring will require to be updated based on question from questionnaire.)

22 Mock Figures

Genentech, Inc.
Protocol: GP41341

FIGURE 14.2.1.1.1
Plasma Pharmacokinetic Concentrations: Entrectinib
Linear/Linear Scale
Arithmetic Mean (\pm Arithmetic SD) Values: PK Population
Part 1

[figure not shown]
Note: Data in the above graph are presented in listing 16.2.5.1.4

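### No planned table counts the subjects per formulation with any post-dose QTcF outlier, although the incidence of ECG abnormalities is a secondary endpoint

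*SAP*

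**What the plan says.** Protocol 2.2 lists as a safety endpoint "Incidence of abnormalities in laboratory safety tests, physical examinations, 12-lead ECGs and vital sign measurements". SAP 4.2.2 repeats it for both parts.

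Under Protocol 4.5.6, "Single ECG recordings will be obtained at specified time points, as outlined in the schedule of activities". The post-dose times are 2, 6, 48 and 96 h (SAP Appendix 1). The same section allows extra ECGs when indicated. If QTcF after dosing exceeds 500 ms, or is 60 ms above baseline, then "another ECG must be recorded, ideally within the next 5 minutes, and ECG monitoring should continue until QTcF has stabilized on two successive ECGs". Protocol 4.6.1 includes among its grounds for discontinuing study treatment a QTcF above 500 msec or an "increase in QTcF interval of >60 msec from baseline (confirmed following a repeat ECG").

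On reporting, SAP 10.6.1 says the QTcF categories of Table 6 "will be summarized by time point. Percentages will be based on the number of subjects with measurements at the relevant time point". The mock of Table 14.5.1.2.2 has rows for baseline and the four post-dose times, by treatment, and nothing that combines times. SAP 10.6.2 then states that "data from unscheduled ECG assessments will also be listed and flagged with a '#' to indicate it will not be used in the summary statistics". The same section plans a listing of every ECG with change from baseline and flags, and a separate by-subject listing of out-of-range values.

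**The concern.** An incidence is a count of subjects: how many, on a given formulation, had an abnormal QTcF at least once after dosing. The SAP counts adverse events in that way, each subject once per treatment (SAP 10.3.1). For measured QTcF it gives only separate snapshots, so the endpoint as worded has no summary table behind it.

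The exclusion of unscheduled ECGs adds a second gap. The ECGs taken because a QTcF looked long, or because the investigator saw a reason to look, do not enter the category table. If the highest value occurs on one of them, the matching column does not show it.

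The stake is moderate. QT prolongation of Grade 2 or higher is an adverse event of special interest (Protocol 5.2.3), so readers of the study report will look for a per-formulation QTcF count. Without a rule set in advance, whoever makes that count from the listings must decide, with open-label data in hand, whether unscheduled and repeat readings belong in it.

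**Working it through.** The plan states no figure on this point, so there is none to reproduce. The check is of the text first, then of how much the planned rows can tell.

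**1. Does the exclusion reach the category table?** Yes. SAP 10.6.2 excludes unscheduled ECGs from summary statistics, and the SAP's Index of Tables titles the table "ECGs QTcF Categorical Data Summary Statistics: Safety Analysis Population Part 1". One exception exists: SAP 14.1 allows an unscheduled value to stand in for a missing baseline.

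**2. What happens to a repeat or unscheduled reading?**

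- *Scheduled reading above 500 ms, repeat lower.* The scheduled value stays in the >500 column. As a table of measured values that is correct.
- *Scheduled reading at or below 500 ms but with a rise large enough to trigger a repeat, and the repeat above 500 ms.* The subject already appears in the increase columns at that time (>60 msec, or 30-60 msec if the rise is exactly 60). Only the >500 column misses the subject.
- *All scheduled readings unremarkable, outlier seen only on an optional unscheduled ECG.* The subject's outlier appears nowhere in the table.

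**3. Can the per-subject count be recovered from the rows?** Let c₁ to c₄ be the numbers of subjects in a given outlier category at 2, 6, 48 and 96 h, and S the number with that outlier at any of those times. Then

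max(c₁,…,c₄) ≤ S ≤ min(N, c₁+c₂+c₃+c₄).

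With the planned enrolment of 15 in Part 1 and 16 in Part 2 (SAP 5.2), and illustrative counts:

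| Counts at 2, 6, 48, 96 h | S | N = 15 | N = 16 |
|---|---|---|---|
| 1, 1, 1, 1 | 1 to 4 | 6.7% to 26.7% | 6.3% to 25.0% |
| 2, 2, 1, 1 | 2 to 6 | 13.3% to 40.0% | 12.5% to 37.5% |

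For example, 1/15 = 6.7% and 4/15 = 26.7%. In the first line the lower end is one subject abnormal four times, and the upper end is four subjects abnormal once each. The rows are identical in the two cases.

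**4. The same point as rates.** Assume an outlier rate p at each time; the documents give none, so 2%, 5% and 10% are chosen only to show a range. If the same subjects recur, the any-time incidence is p. If the times are independent, it is 1 − (1 − p)⁴, which gives 7.8%, 18.5% and 34.4%.

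**5. Related loose ends.**

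- The percentage denominator is the subjects measured at the time point in SAP 10.6.1, but the footnote to the mock table says "N# is the total number of subjects in the relevant treatment and is used as the denominator for" the percentages.
- The '#' flag means unscheduled and unused in SAP 10.6.2, but outside the time window in the mock vital-signs listing that also serves as the model for the ECG listing.
- A repeat about 5 minutes later can fall inside the ±15-minute window of Protocol 4.5.6, and the SAP has no rule for two ECGs in one window.

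**The case against.** The strongest reply is that nothing is lost. Every ECG, unscheduled ones included, is listed by subject with treatment and flags for out-of-range values and for increases of 30-60 and >60 msec. With 15 or 16 subjects per part, the count is a short read. QT prolongation of Grade 2 or higher is also tabulated by subject and treatment as an adverse event of special interest (SAP 10.3.1.6). Protocol 4.6.1 places confirmed QTcF cases under serious or severe adverse events, so they should reach the adverse event tables as well. This stands, with one limit: those tables count reported events, not measured QTcF in the categories of Table 6. A reader might infer that the per-formulation count can never be obtained; the documents do not support that.

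A reader might also infer that the table is wrong in both directions, because it counts an unconfirmed spike and misses a confirmed event. That does not hold either. The table reports measured values in the ICH E14 categories and does not claim to apply the discontinuation criterion of Protocol 4.6.1. A repeat ECG is called for only after a reading has already met the alarm, so a subject whose alarm came from a scheduled ECG is already in one of the columns.

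Three further points are fair. Leaving unscheduled readings out of summaries is the SAP's general convention, used also for laboratory data and vital signs (SAP 10.4.2 and 10.5.2), and it avoids a bias towards readings taken on suspicion. The safety objective is exploratory. The background is also not alarming: the dog QTc findings were reversible and at high doses (Protocol 1.1.1), and the patient studies are reported as showing no evidence of QTc prolongation (Protocol 1.1.2.1). These limit the weight of the point but do not supply the missing count.

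**Conclusion.** The point holds as a reporting gap on a secondary safety endpoint. The number of subjects per formulation with any measured post-dose QTcF outlier is not tabulated and cannot be derived from the planned rows; it has to be counted by hand from the listings. In the simplest case the rows leave it open between 1 and 4 subjects. A value above 500 ms seen only on a repeat, or any outlier seen only on an optional unscheduled ECG, is missing from the matching column.

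The size is illustrative. It assumes the planned enrolment contributes to each treatment and uses invented counts, since the documents contain no ECG results. If no subject has an outlier, the gap has no practical effect. The primary pharmacokinetic analysis is untouched. This is a cheap improvement worth making, not a flaw that threatens the trial's conclusions.

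**What to change.** - In Tables 14.5.1.2.2 and 14.5.2.2.2, keep the by-time-point rows and add, per treatment, a row 'Any post-dose (worst value)' with the subject as the unit. Use all scheduled, repeat and unscheduled ECGs from dosing until the next period's pre-dose ECG or, in the last period, the last recorded ECG.
- In SAP 10.6.2, limit the '#' exclusion to the by-time-point statistics, and give '#' one meaning across the text and mock listings.
- State the denominator of the new row, and reconcile SAP 10.6.1 with the mock footnote on the existing rows.
- Optionally, footnote which cases above 500 ms or with a rise above 60 ms were confirmed on a repeat ECG, in the protocol's own terms.

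The cost is SAP wording and one row per treatment in two tables, with no new ECGs and no change to any clinical rule. The downside is that the worst-value row may run somewhat high, because unscheduled ECGs are taken when a problem is suspected. The retained by-time-point rows and the optional footnote let the reader judge that.
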